6.6. Statistical methods

The data documented in this study and the parameters measured will be evaluated and compared. Continuous data will be summarized with standard descriptive statistics (i.e. mean, SD, median, interquartile range [IQR], minimum and maximum). Categorical data will be summarized by frequency and percentage. 95% confidence intervals (CIs) will be provided as relevant.

All data will be presented by treatment arm and overall and, if relevant, by study visit.

Statistical test will be performed for between-arm differences in demographic and baseline features (medical and efficacy data).

Medical history and adverse events (AEs) will be described according to System Organ Classes (SOC) and Preferred Terms (PT) using the Medical Dictionary for Regulatory Activities (MedDRA) and will be presented by treatment arm. Previous/concomitant medications will be presented by treatment arm using the World Health Organization Drug Dictionary (WHO-DD).

All analyses will be performed using SAS® software, the latest applicable version..

A p-value equal to or lower than 0.05 will be considered statistically significant.

6.6.1. Efficacy analyses

6.6.1.1. Primary analysis

The primary variables will be analyzed presenting descriptive statistics (mean, SD, median, IQR, minimum and maximum for total [REDACTED] endpoint and count and percentage for IGA success rate endpoint) overall, by treatment arm and, if deemed relevant, by study visit.

Subgroup analyses will be performed for: gender (M; F), age (≥ 9 and ≤ 18 years; vs ≥ 19 and < 50 years; and also in the following subgroups ≤ 12 ; 13 to 18; ≥ 19), IGA/PGA, Race/ethnicity (White; Black; Asian, Latino; other); Fitzpatrick skin type; country.

Absolute and relative differences in terms of total [REDACTED] between baseline and EoT will be also presented.

Estimands for the primary Endpoint 1 (E1)

The estimand for the primary E1 is defined as follows:

1. Treatment: 12 weeks administration of NAC-GED-0507 gel [REDACTED]% or vehicle gel.
2. Target population: Male and female patients aged ≥ 9 and < 50 years affected by facial acne vulgaris. Full Analysis Set.
3. Variable: relative change from baseline in total [REDACTED] (inflammatory plus non-inflammatory) at V5/Wk12 on the face.
4. Intercurrent events (ICEs) and strategies to handle them:
 - Treatment discontinuation

- Study withdrawal
- Use of prohibited medications listed in section 5.4.7

A treatment policy strategy will be applied where all observed values will be used regardless of the occurrence of the ICEs. Missing data due to any reason will be handled by using a LOCF imputation

5. Population-level summary: the difference in the relative change from baseline to V5/Wk12 in total [REDACTED] between the two treatment groups will be assessed by an independent t-test (or a Wilcoxon test if the Normality is violated). A p-value equal to or lower than 0.05 will be considered statistically significant.

Estimands for the primary Endpoint 2 (E2)

The estimand for the primary E2 is defined as follows:

1. Treatment: 12 weeks administration of NAC-GED-0507 gel [REDACTED]% or vehicle gel.
2. Target population: Male and female patients aged ≥ 9 and <50 years affected by facial acne vulgaris. Full Analysis Set.
3. Variable: proportion of patients with an IGA success at V5/Wk12.
4. Intercurrent events (ICEs) and strategies to handle them:
 - Treatment discontinuation
 - Study withdrawal
 - Use of prohibited medications listed in section 5.4.7.

A treatment policy strategy will be applied where all observed values will be used regardless of the occurrence of the ICEs. Missing data due to any reason will be handled by using a LOCF imputation

5. Population-level summary: the difference in terms of the proportion of patients with an IGA success at V5/Wk12 between the two treatment arms will be assessed with an independent Chi-Square test (or Fisher exact test if the successes in one of the two treatment groups is lower than 5). A p-value equal to or lower than 0.05 will be considered statistically significant

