5.2. Discussion of trial design, including the choice of control groups

A double-blind design (patients and investigators blinded) is chosen to ensure the study assessments are carried out without bias.

Parallel group comparison is a common method and provides optimal conditions for examining efficacy (ICHE9 Guidance, Statistical Principles for Clinical Trials).

A randomization in a 1:1 ratio to either NAC-GED-0507 gel [REDACTED]% or vehicle gel is chosen as considered the most reliable and impartial method of determining differences between the IMP vs. vehicle gel.

Block randomization is a commonly used technique in clinical trial design to reduce bias and achieve balance in the allocation of participants to treatment arms. This method increases the probability that each arm will contain an equal number of individuals by sequencing participant assignments by block.

The randomization will also be stratified by age group to ensure the comparability of the two treatment arms within each stratum.

The vehicle gel, containing the same excipients as NAC-GED-0507 [REDACTED]% without the active substance, will serve as an external validity check for the study results and will show what an agent-free therapy contributes to in terms of efficacy and safety.

To evaluate a therapeutic effect, both clinical assessments using counting of inflammatory and non-inflammatory lesions and the IGA/PGA to assess the overall acne severity will be used as primary measures which largely follows the S-3 Guideline for Treatment of Acne (Nast A, 2016) and the FDA Draft 'Guidance for Industry - Acne Vulgaris: Establishing Effectiveness of Drugs Intended for Treatment' (May 2018). This combination allows for a balanced approach toward the evaluation of acne severity.

Experience has shown that once daily application on 84 consecutive days is adequate for the purpose of this study. If a treatment success occurs, it is largely seen during this time period of 12 weeks.

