5.3.2. Justification of patient population

Acne occurs primarily during adolescence, with a prevalence that may reach 95% (Maronas, Jimenez, 2016). Acne may also be the first sign of pubertal maturation; the presence of acne in a patient, independently on patient's age, can occur when sebaceous glands are functional and have an impact on the skin barrier properties through sebogenesis; acne in early childhood is very rare. Generally, girls have an earlier onset, with an average age between 11 and 13 years, compared with boys, between 13 and 14 years, with more intense and severe forms (Bhate et al 2013).

In agreement with the Scientific Advice from EMA and with the opinion of Paediatric Committee (PDCO) on the Paediatric Investigation Plan, the Sponsor plans to run the current clinical study in acne patients ≥ 9 and ≤ 50 years old. Due to the low prevalence of acne in pediatric subset from birth to less than 9 years, and the fact that most diagnosed with infantile acne have a moderate course at best requiring no treatment, the enrollment of patient under the age of 9 would result in a lack of feasibility and PDCO granted a waiver for this age range.

Since acne in patients 9 to 14 years is usually less severe in grade, inclusion of patients with IGA 2 will be allowed for this age class.

The non-clinical studies package confirms the safety profile of NAC-GED-0507 and that it has no effects on the reproductive system in case of systemic exposure at large exposure margins for

adolescents and children. It includes a 13-week repeat-dose dermal tolerance study in minipigs. The age of the minipigs at the start of the study corresponds to that of human adolescents. This package also encompasses toxicity studies, which include chronic toxicity, and a 39-week dermal tolerance and toxicity study. The latter was performed on minipigs aged nine weeks at the beginning of the treatment, corresponding to children aged nine years old.

This study expects little or no dermal absorption. This assumption is based on available clinical and non-clinical data, as well as a Phase 1 open-label clinical study in patients affected by acne with NAC-GED-0507 1% gel (Study NAC-GED-0507-ACN-02-17, EudraCT 2017-003796-58), performed in patients aged 12-30.

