6.5. Rationale for the sample size

The sample size is based on the two co-primary endpoints: relative change from baseline in total lesion count on the face (inflammatory plus non-inflammatory) and IGA success at V5/Wk12 to reach a power of 90% at a level of 0.05, since this are considered the most relevant clinical endpoints.

The formal calculation of sample size is based on the paper from T. Sozu et al. Sample size for co-primary continuous and binary endpoint (2012), assuming the normality of the relative change from baseline distribution and making the following assumptions:

- an error I type of ■%
- a statistical power of ■%
- a relative change from baseline in total lesion count on the face at V5/Wk12 in the IMP 2-V arm (placebo arm) of ■% (data retrieved from the Study NAC-GED-0507-ACN-01-18)
- a Standard Deviation (SD) of the difference between treatment arms of ■% (data retrieved from the Study NAC-GED-0507-ACN-01-18).
- a rate of IGA success on the face at V5/Wk12 in the IMP 2-V arm (placebo arm) of ■% (data retrieved from the Study NAC-GED-0507-ACN-01-18)
- a difference between the two treatment arms in terms of the relative change from baseline in total lesion count on the face (inflammatory plus non-inflammatory) at V5/Wk12 equal to or greater than ■% and a difference in IGA successes equal or greater than ■% (data retrieved from the Study NAC-GED-0507-ACN-01-18).

A sample size of 366 evaluable patients (183 in each treatment arm), will be adequate to find a significant difference between the two treatment arms in terms of the relative change from baseline in total lesion count on the face (inflammatory plus non-inflammatory) at V5/Wk12 and in IGA successes.

Considering a drop-out rate close to ■% of non-evaluable patients for any reason, a total of 400 patients will have to be enrolled in the study (sample allocation ratio 1:1).

A second pivotal Phase 3 study (NAC-GED-0507-ACN-01-23-B) with an identical study design to the present study is planned to be performed with an equivalent sample size of 400 patients in total.

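### Both co-primary tests are unadjusted although age is stratified and baseline severity is recorded: valid, but precision is given away

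*Protocol*

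**What the plan says.** The tests are part of the protocol's estimands, so they are not a detail left to the SAP. In Section 6.6.1.1 the E1 difference in relative change "between the two treatment groups will be assessed by an independent t-test", with Wilcoxon as the fallback. For E2, the difference in success proportions "between the two treatment arms will be assessed with an independent Chi-Square test", with Fisher as the fallback. The synopsis repeats both. In Section 6.6.1.3 the per-protocol analysis repeats the primary analysis, and the multiple-imputation analyses use the same unadjusted tests. No planned analysis of either co-primary contains a covariate or stratum.

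On design, Section 5.2 states: "The randomization will also be stratified by age group to ensure the comparability of the two treatment arms within each stratum". Sections 5.1 and 5.4.3 name one stratum, ages 9 to <12, at 5% or 20 patients. Section 5.3.3 admits patients over 14 at IGA 3 or 4 and those aged 9 to 14 at IGA 2 or more. Section 5.3.2 explains that "inclusion of patients with IGA 2 will be allowed for this age class". In Section 6.6.1.1, age, IGA/PGA and country appear only as subgroup variables.

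Section 6.6 adds: "Statistical test will be performed for between-arm differences in demographic and baseline features". Nothing says what follows from a significant result.

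**The concern.** Facial lesion count and IGA are measured at baseline on everyone and plausibly predict week-12 outcome. A two-sample test leaves the variation they explain in the error term. Trial success needs both co-primaries, so lost precision on either lowers the chance of success.

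E2 is the clearer case. Success means reaching 0 or 1, which is at least one grade down from IGA 2, two from IGA 3 and three from IGA 4. The chi-square test pools these patients, and baseline IGA is not a randomisation factor, so the mix can differ between arms by chance. Testing baseline characteristics does not help: in a randomised trial a significant difference is a chance finding, and detecting it does not correct the estimate.

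**Working it through.** **The plan's own figure.** Section 6.5 sizes the trial "to reach a power of 90% at a level of 0.05": "A sample size of 366 evaluable patients (183 in each treatment arm"). The effect sizes, SD, vehicle rate and dropout are redacted and sidedness is not stated, so 183 cannot be formally reproduced. It is consistent with E2 as the limiting endpoint, taking two-sided 0.05 and no continuity correction:

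n per arm = [1.960√(2p̄(1−p̄)) + 1.282√(p₁(1−p₁)+p₂(1−p₂))]² / (p₂−p₁)²

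- 20% vs 35%: (1.238 + 0.798)²/0.0225 ≈ 184.1, so 185.
- 25% vs 41%: (1.303 + 0.840)²/0.0256 ≈ 179.4, so 180.

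**E1.** With multiple correlation R between covariates and outcome, ANCOVA multiplies the variance by 1−R². If the unadjusted test has 90% power at 183 per arm, adjusted power = Φ(3.242/√(1−R²) − 1.960). R is assumed; the protocol gives none.

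| R | Variance cut | SE cut | Power | n per arm for 90% |
|---|---|---|---|---|
| 0.1 | 1% | 0.5% | 90.3% | 182 |
| 0.2 | 4% | 2.0% | 91.1% | 176 |
| 0.3 | 9% | 4.6% | 92.5% | 167 |
| 0.5 | 25% | 13.4% | 96.3% | 138 |

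If the 90% is joint power, each endpoint starts higher. With equal and independent endpoints, each has √0.90 = 94.9%. The first term becomes 1.960 + 1.632 = 3.592, and R = 0.2-0.3 gives about 95.6-96.5%, a smaller gain in points.

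**Does the E2 definition already adjust for baseline?** Patients over 14 must reach 0 or 1 and fall at least 2 points. They enter at 3 or 4, and 3−1 = 2 and 4−1 = 3, so reaching 0 or 1 always meets the second condition. The clause therefore makes no allowance for baseline severity.

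**E2 power.** Simulation with 183 per arm, 200,000 runs and baseline IGA left to chance compared chi-square with Cochran-Mantel-Haenszel (CMH) stratified by baseline IGA. All mixes and rates are assumed.

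| IGA mix | Vehicle success | Added by active (points) | Chi-square | CMH | Gain (points) |
|---|---|---|---|---|---|
| 3/4: 85/15% | 28/10% | 16.5/10 | 88.9% | 89.6% | 0.6 |
| 3/4/2: 75/15/10% | 26/8/50% | 16.5/10/15 | 88.2% | 89.6% | 1.5 |
| 3/4: 70/30% | 32/10% | 18.5/10 | 90.5% | 92.2% | 1.7 |
| 3/4: 50/50% | 38/8% | 20/10 | 88.1% | 92.4% | 4.3 |

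Gains are taken from the unrounded powers.

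**Age stratum alone (5%).** With vehicle success of 25, 40 or 60% in the stratum and 25% elsewhere, stratifying changes E2 power by about 0, 0.1 and 0.5 points.

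**Chance imbalance, E2.** The 95% range of the between-arm difference in a share s is ±1.96√(2s(1−s)/183). For s = 15% it is ±7.3 points, and for 30% it is ±9.4. With an assumed 20-point success gap between IGA 3 and 4, the risk difference moves by 1.5 or 1.9 points.

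**Validity.** With no treatment effect, the simulated type I error of the chi-square test was 0.047 to 0.050 in every scenario. The lowest value came under age-stratified randomisation and is slightly conservative.

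**The case against.** The strongest defence is that nothing here is an error. Two-sample tests are valid under 1:1 randomisation. Stratified allocation does what Section 5.2 asks of it, and Section 6.5 mentions no covariate, so planned power does not depend on adjustment. All of that stands.

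It also stands that E1 is already scaled by the baseline count, so the further gain from that covariate may be modest. The named age stratum contributes almost nothing. Chance imbalance is already inside the unadjusted standard error: at 25% vs 41% the 95% half-width is 1.96√((0.1875+0.2419)/183) = 9.5 points, and the 1.5-1.9 point shift is part of it.

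Power may also be ample. At the Phase 2b subgroup rates in Section 2 (20.9% vs 41.4% and 28.8% vs 50.8%), E2 would need 106 or 102 per arm. Those are proxies, because the sizing inputs are redacted.

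One part of the defence fails. E2 cannot be said to account for baseline IGA through its 2-point clause, because that clause never binds on patients who enter as Section 5.3.3 requires.

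A reader might infer three stronger things that the documents do not support:

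- Omitting the age stratum does not inflate type I error.
- The trial is not shown to be undersized. The R = 0.5 row has no support in the protocol.
- The baseline significance tests are not presented as a substitute for adjustment, and no decision hangs on them.

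**Conclusion.** The point holds as an efficiency recommendation. The protocol fixes unadjusted tests for both co-primaries and all their sensitivity analyses, and leaves unused information it already collects. The consequence is a somewhat wider interval and an estimate not corrected for chance imbalance, in E1 as well as E2. Neither endpoint is biased and the significance level is sound.

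The likely size is small: about 1 to 2.5 power points for E1 at R = 0.2-0.3, and about 1 to 2 points for E2 with 15-30% of patients at IGA 4, rising to about 4 points at 50%. These figures assume two-sided testing, 183 per arm and, for E1, exactly 90% unadjusted power. The correlations, IGA mix and success rates by grade are also assumed, and the protocol cannot confirm them. The case for changing rests on the very low cost, not on a large demonstrated loss.

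**What to change.** Amend the synopsis and Sections 6.6.1.1 and 6.6.1.3 before unblinding:

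- **E1:** make ANCOVA of relative change on arm, baseline total facial lesion count and age stratum (9 to <12; ≥12) the primary analysis. Keep the unadjusted t-test or Wilcoxon as supportive, so that the primary method no longer switches on a normality check.
- **E2:** make a covariate-standardised risk difference from logistic regression, adjusted for baseline IGA and age stratum, the primary analysis. The alternative is CMH stratified by baseline IGA only, merging IGA 2 with 3 if sparse. Keep the unadjusted chi-square as supportive.
- **Country:** it may enter as a pooled main effect but not as a CMH cross-stratum. Three IGA grades × two age strata × four countries (synopsis minimum) or five (Section 5.1 minimum) would make 24 or 30 cells, with only 20 patients planned in the youngest stratum.
- **Baseline tables:** drop the significance tests in Section 6.6 and report descriptively.

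The cost is wording, slightly more analysis work and reliance on a pre-specified model. All covariates are already collected.

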6.6.1.2. Secondary analyses

Secondary variables will be analyzed presenting descriptive statistics overall, by treatment arm and, if deemed relevant, by study visit.

Subgroup analyses will be performed for: gender (M; F), age (≥ 9 and ≤ 18 years; vs ≥ 19 and < 50 years; and also in the following subgroups ≤ 12 ; 13 to 18; ≥ 19); IGA Score at Baseline, Race/ethnicity (White; Black; Asian, Latino; other); Fitzpatrick skin type; country.

All statistical tests that will be applied, if any, will have exploratory purposes only.

The analyses of the secondary endpoints will be conducted on the FAS and PPS sets.

LOCF imputation methodology will be used to impute missing values for the lesions count and the IGA in the FAS.

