5.3.3. Inclusion criteria

The following criteria have to be met for inclusion of a patient in this trial:

1. *Informed consent obtained**

* Written informed consent, before any study-related procedure, personally signed and dated by the patient if the patient is ≥ 18 years old (or different age based on local regulations), or signed and dated by the parents or the legal guardian(s) (or only one parent depending on local regulations) if the patient is ≥ 9 to < 18 years old (or different age based on local regulations). An additional informed assent form must be signed by patient if ≥ 9 to < 18 years old (or different age based on local regulations) to confirm his willingness to participate in the study. If the patient becomes 18 years of age (or different age based on local regulations) during the study, the patient must provide written informed consent at that time to continue study participation.

2. *Sex and age*: Male and female patients aged ≥ 9 and < 50 years

3. *Diagnosis at screening and baseline visits*:

a) Patient affected by facial acne vulgaris with:

Investigator's Global Assessment (IGA) score:

- equal to 3–4 if patient is > 14 and < 50 years old
- ≥ 2 if the patient is ≥ 9 and ≤ 14 years old

Face Inflammatory lesions: ≥ 20 and ≤ 100 inflammatory lesions (papules and pustules) and ≤ 1 nodules on the face

Face Non-inflammatory lesions: ≥ 20 and ≤ 100 non-inflammatory lesions (open and closed comedones) on the face

b) Patients affected also by truncal acne (optional criteria):

The patient has a truncal acne on areas of the trunk (shoulders, upper back and upper anterior chest) accessible for patient's self-application of study medication with a severity grade equals to 2 or 3 on the Physician Global Assessment (PGA) scale.

The patient has a minimum of 20 inflammatory lesions (papules and pustules) and 20 non-inflammatory lesions (open and closed comedones), but no more than 100 non-inflammatory lesions on areas of the trunk (shoulders, upper back and upper anterior chest) reachable to patient's self-application of study medication at screening and baseline

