5.4.3. Assignment of treatments and randomization

Patient identification

Upon signature of informed consent each patient receives an 8-digit patient screening number via IWRS, which is composed of:

Digits 1 and 2: country code

Digits 3 and 4: trial site (01, 02, 03, etc.)

Digits 5, 6, 7 and 8: hyphen and individual screening number within the site (consecutively in the order of screening within the site: 001, 002, etc.)

The patient will keep the patient number as identifier throughout the trial (i.e. IT01-001).

Treatment assignment

Only patients who satisfy all the inclusion and none of the exclusion criteria will be randomized.

Patients will be randomized to one of 2 treatment arms:

IMP 1 arm

N-Acetyl-GED-0507-34-Levo ■% gel (■ mg/100 mg): 200 patients

IMP 2 Vehicle arm (V)

N-Acetyl-GED-0507-34-Levo corresponding vehicle: 200 patients

Treatment allocation will be on a 1:1 ratio in a blinded manner.

Enrollment will be performed competitively between all sites until approximately 400 patients are randomized in the trial to have 366 evaluable patients.

The randomization schedule will be constructed using SAS (Statistical Analysis System, SAS, Cary, NC).

Randomization will be stratified to include:

- Subset 9 to < 12 years: 5% of patients, corresponding to 20 patients.

Randomization

Patients who are eligible for enrollment into the trial will be randomized and assigned a randomization/kit number (randomization number = kit number). This randomization/kit number is different from the patient number and will only serve for treatment assignment, not for patient identification. The randomization/kit number will be recorded in the eCRF and the source documents, thus an allocation is possible at any time.

The patients will be randomized at V2/Day 1 by the interactive web response system (IWRS) to ensure study medication assignment according to stratification.

Patient kits will be dispensed according to the randomization/kit number assigned.

The treatment group designation will remain blinded to the sites until the final database is locked.

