5.5.2. Clinical Assessments

5.5.2.1. Lesion Counts

Non-inflammatory lesions (closed and open comedones), inflammatory lesions (papules, pustules, and nodules, if applicable) on the face, including the nose, and on the trunk (shoulders, upper back and upper anterior chest) will be counted and recorded separately at each scheduled site visit throughout the study.

Lesions are defined as follows:

Non-inflammatory lesions:

- Comedones – open (blackheads)
- Comedones – closed (whiteheads).

Inflammatory lesions:

- Papules – raised inflammatory lesions with no visible purulent material
- Pustules – raised inflammatory lesions with visible purulent material
- Nodules – any circumscribed, inflammatory mass greater than or equal to 5 mm in diameter with or without cystic changes.

The investigator/evaluator should use standard, good lighting and magnification as necessary to visualize lesions and a systematic counting procedure to ensure consistent and accurate counts.

The overall number of inflammatory lesions and non-inflammatory lesions for each of the two regions (face and trunk) will be reported separately in the eCRF. The overall number of total lesions

(inflammatory plus non-inflammatory lesions) will be calculated by the electronic data capture (EDC) system.

For the face, the total lesions will be calculated as the sum of inflammatory plus non-inflammatory lesions, including the nose.

For the trunk, the total lesions will be calculated as the sum of inflammatory plus non-inflammatory lesions of the anterior part of the trunk, excluding the neck and axillary regions.

Assessments per patient should be done by the same trained investigator throughout the study, if possible, to minimize the possibility for introduction of bias.

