6.2. Analysis sets and type of analysis

Screened Analysis Set (SCR)

This analysis set includes all patients who signed the informed consent form and received a screening number, regardless of whether they completed all the screening procedures.

Enrolled Set (ENR)

All patients included in the study, excluding screening failure.

Randomized Set (RND)

All enrolled patients who are randomized to a treatment arm.

Full Analysis Set (FAS)

The Full Analysis Set (FAS) includes all randomized patients who receive at least one dose of the study medication and have at least one valid post-baseline efficacy assessment for both primary endpoints.

The analyses on FAS will be performed with the Intention-To-Treat (ITT) principle.

Per-Protocol Set (PPS)

The Per-Protocol Set (PPS) comprises all patients included in the FAS who complete the study without major protocol deviations. Major protocol deviation will be identified in the SAP and/or during a blind medical review.

The analysis of efficacy will be conducted on the FAS and PPS sets, with the FAS considered as the primary set for statistical analysis, based on treatment as randomized.

Safety Set (SS)

The Safety Set (SS) includes all patients who received at least one dose of study treatment. Safety analyses will be performed on the Safety Set based on treatment as received.

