6.7. Handling of dropouts and missing data

Last observation carried forward (LOCF) imputation methodology will be used to impute missing values for the lesions count and the IGA/PGA in the FAS set.

7. Adverse events

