9. For patients aged 9 to < 12 only, a phone contact will be kept at Wk2 and Wk10 (with the presence of parents/guardian(s) who gave consent or only one parent depending on local regulations), to check concomitant medications/therapies and AEs and assessment of local tolerability by local signs/symptoms (the patient will also be questioned if he/she experienced any of them in the last 24 hours). Patient will also be questioned on compliance to study medication. The outcome of the contact is entered in the eCRF
10. ██████████
11. ██████████
12. Patients who complete 12 weeks of treatment will be eligible to continue treatment with NAC-GED-0507-34-Levo ██████% gel in a separate open-label long-term study (GEDACNE-LT)
13. V6 will not be performed for patients who continue the open-label long-term treatment with NAC- GED-0507-34-Levo ██████% gel in GEDACNE-LT study
14. After baseline visit, the PGA will be evaluated only if the trunk is treated (PGA score should be 2 or 3 at screening/baseline visit as per inclusion criteria).
15. All study visits for school age children should be planned outside of school hours
16. At baseline, the presence or absence of signs/symptoms in the past 14 days will be also collected
17. Presence or absence of overall application site irritation at the baseline visit will be collected.
18. Height to be measured for minors only

EoT = End of treatment

ETV = Early termination visit (Withdrawal)

13. Appendix B

Investigator signature

Title A phase III study to assess efficacy and safety of N-Acetyl-GED-0507-34-LEVO gel █%, applied once daily for 12 weeks in patients with acne vulgaris (GEDACNE-1)

Protocol no: NAC-GED-0507-ACN-01-23-A

Protocol version: Final V2.0 (UK only)

Protocol date: 24JAN2025

I confirm with my signature

- that I agree to conduct the trial in accordance with regulations as laid down in this clinical trial protocol/amendment, in the currently valid revision of the Declaration of Helsinki and in the ICH-GCP guideline and applicable national laws and regulations. Changes to this protocol require written agreement of both investigator and Sponsor
- that I have acquainted myself with the results of the pharmacological and toxicological trials of the investigational product and the results of other trials as described in the investigator's brochure, or other appropriate information.

[figure not shown]
I agree:

- to provide direct access to source data/documents (source document verification)

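### The five TRUNK endpoints are assigned to the FAS and PPS, which include patients whose trunk is never treated; a trunk analysis set is needed

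*Protocol*

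**What the plan says.** - **Population for the trunk endpoints.** Section 6.3.2 lists five TRUNK endpoints as secondary: four on lesion counts and one on PGA success. Section 6.6.1.2 states: "The analyses of the secondary endpoints will be conducted on the FAS and PPS sets". Section 6.2 defines no truncal set.
- **Who is in the FAS.** Section 6.2 asks for at least one dose and that patients "have at least one valid post-baseline efficacy assessment for both primary endpoints". Both primary endpoints are facial (section 6.3.1). The PPS is a subset of the FAS with no trunk condition.
- **Who has a treated trunk.** Inclusion criterion 3b in section 5.3.3 reads "b) Patients affected also by truncal acne (optional criteria". Sections 5.1 and 5.4.1 put gel on the trunk only where it is affected by acne. Table 1 lists two kit types, face and face + trunk.
- **Trunk lesion counts.** Section 5.5.2.1 says that lesions on the face and on the trunk "will be counted and recorded separately at each scheduled site visit throughout the study". Section 6.3 says much the same. Neither limits this to treated trunks.
- **PGA.** The Appendix A schedule marks PGA for everyone at screening and baseline. Footnote 14 then says: "After baseline visit, the PGA will be evaluated only if the trunk is treated".
- **Imputation.** Section 6.7 uses LOCF to "impute missing values for the lesions count and the IGA/PGA in the FAS set". The LOCF sentence in section 6.6.1.2 names lesion counts and IGA but not PGA.

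**The concern.** A trunk endpoint is meant to show what the gel does on the trunk. A patient who applied gel only to the face carries no information on that, in either arm. The stated population rule nevertheless puts such patients into all five trunk comparisons, by two routes:

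- **Counts (four endpoints).** Face-only patients have observed trunk counts at each visit as the protocol is written. Their changes enter the arm means although nothing was applied there. This does not depend on how LOCF is read.
- **PGA success (one endpoint).** Face-only patients have a baseline PGA and none afterwards. Whether they count depends on whether that baseline grade is carried forward. If it is, they can never meet the required two-grade improvement.

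At stake are the trunk estimates that a pivotal trial will report. They would describe a mixture of treated and untreated trunks, in a proportion that the protocol does not fix or predict.

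**Working it through.** **Plan's own figure.** There is none for the trunk endpoints. The 366 evaluable patients (183 per arm, section 6.5) were sized for the facial co-primaries. The planning rates are redacted, so 366 cannot be rebuilt, and the point does not depend on it. Below, 183 serves only as the FAS size per arm.

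**Inputs**
- n = 183 per arm (section 6.5); two-sided 5% test (level from section 6.5, sidedness assumed).
- s = share of FAS patients with a treated trunk. The protocol gives no figure; 20%, 30% and 50% are assumed.
- Truncal PGA success 40% vs 20%, assumed.
- As a second illustration, the Phase 2b facial IGA rates for patients over 18 (section 2), 50.8% vs 28.8%, as a stand-in for truncal rates.

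**1. Count endpoints.** Let D_T be the between-arm difference in mean change for treated trunks and D_U that for untreated trunks. With equal shares in both arms, the FAS difference is

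s × D_T + (1 − s) × D_U.

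No gel reaches the trunk in the second group, so D_U should lie near zero in expectation. The FAS difference then tends to s × D_T. The documents give no truncal count data, so no figure is put on this.

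**2. PGA endpoint, if baseline is carried forward.** Success needs grade 0 or 1 and at least two grades of improvement (section 6.3.2). An unchanged grade fails whatever its value. The FAS rates are therefore s × p1 and s × p2, and the difference is s × (p1 − p2).

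Power uses the normal approximation for two proportions, Φ[(d − 1.96 × se0) / se1], with se0 the pooled and se1 the unpooled standard error. It is taken once with 183 × s per arm at the undiluted rates, and once with 183 per arm at the diluted rates.

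| s | Treated trunks only | Whole FAS | Difference in FAS | Power, treated only | Power, FAS |
|---|---|---|---|---|---|
| 20% | 40% vs 20% | 8% vs 4% | 4 points | 46% | 36% |
| 30% | 40% vs 20% | 12% vs 6% | 6 points | 63% | 52% |
| 50% | 40% vs 20% | 20% vs 10% | 10 points | 85% | 77% |

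With the stand-in rates, the 22.0-point difference becomes 4.4 points at s = 20% (0.2 × 22.0) and 11.0 at s = 50% (0.5 × 22.0).

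Two limits on this arithmetic:
- The ratio of the success rates does not change (40/20 = 12/6 = 2), and the test statistic falls by less than the difference does. The factor is about √[(1 − p)/(1 − s × p)], with p the pooled truncal rate. For p = 0.30 and s = 0.30 it is √(0.70/0.91) = 0.88.
- Truncal involvement is not a stratum (section 5.4.3 stratifies by age only), so the shares differ between arms by chance. The SD of the difference in shares is √[2 × s × (1 − s)/183], which is 4.2 points at s = 20% and 5.2 points at s = 50%. The shrinkage by s holds in expectation, not exactly.

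**3. PGA endpoint, if only post-baseline values are carried forward.** Face-only patients have no PGA outcome and leave the denominator, so nothing is diluted. But the set analysed is then no longer the FAS that section 6.6.1.2 names.

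**The case against.** **The PGA mechanism is not stated.** Nothing says that a baseline value may be carried forward, or that a PGA never scheduled counts as missing. Section 6.7 concerns dropouts and missing data, and a face-only completer is neither a dropout nor missing a scheduled assessment. The LOCF sentence in section 6.6.1.2 leaves PGA out. This stands. A reader might infer that face-only patients will be scored as truncal failures; the text permits that reading but does not establish it.

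**Only one of the five endpoints uses PGA.** This stands too. A reader might apply the PGA figures above to all five, but the four count endpoints are reached by another route and no size can be given for them. That route rests on observed counts, so the PGA objection does not remove it.

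**There are partial safeguards.** LOCF in section 6.7 is limited to the FAS, so the PPS has no stated PGA imputation. The synopsis lists baseline IGA/PGA score as a subgroup for secondary endpoints, which would largely separate truncal patients. Neither is enough. Untreated-trunk counts remain in the PPS, and section 6.6.1.2 lists only baseline IGA as a subgroup.

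**This belongs in the SAP.** Detail may well be there. But the protocol does state the population, so a trunk set in the SAP would depart from that statement.

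**The tests are exploratory.** Correct: section 6.6.1.2 says so. No alpha and no co-primary result depends on them. Descriptive trunk estimates would still be reported.

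**Conclusion.** The point holds in a limited form. As written, the protocol analyses all five TRUNK endpoints in sets that include patients who never applied gel to the trunk. For the four count endpoints this mixes in observed changes from untreated trunks, to an extent that cannot be quantified from the document. For the PGA endpoint there is a loss only if baseline grades may be carried forward. In that case the expected risk difference is the truncal difference times the truncal share: 4, 6 or 10 points instead of 20 at assumed shares of 20%, 30% or 50%, with power 8 to 11 points lower. Both the share and the truncal rates are assumptions.

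The documents do not support a statement that the reported truncal results will be wrong, and the facial co-primary conclusions are unaffected. The change is worth making because it corrects a stated population rule at almost no cost.

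**What to change.** 1. In sections 6.2 and 6.6.1.2, define a trunk analysis set: FAS patients (and, for the supportive analysis, PPS patients) who met criterion 3b at baseline and were assigned trunk treatment, that is, a face + trunk kit. Use it for every TRUNK endpoint. Both conditions are known by Visit 2 (section 5.4.3 has "randomization number = kit number"), so membership can be settled without outcome data.
2. Apply PGA and trunk-count imputation only within that set.
3. State whether a baseline value may be carried forward under LOCF.
4. Align the LOCF sentences in sections 6.6.1.2 and 6.7 on whether PGA is included.

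The cost is a few sentences in the protocol and SAP before unblinding, with no new data. The downside is a smaller denominator: at an assumed 30% share, about 55 patients per arm (0.30 × 183) instead of 183. A reader might infer that face vs face + trunk should also become a randomisation stratum. The point does not require it: a set fixed by baseline status and kit type needs no change to the strata.
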